2.4.6.4 Analyses of vital sign variables

Vital signs parameters are described in [Section 2.1.4.4](#).

- Summaries of baseline, Day 7 and Day 14 (or end of treatment) assessments will be provided for all parameters (except for weight which will be assessed at baseline and D14 only).
- For ECOG performance status, a shift table will be provided for post-treatment evaluation relative to baseline.

For vital sign variables, potentially clinically significant abnormalities (PCSA) values are defined as abnormal values considered medically important by the Sponsor according to predefined criteria/thresholds based on literature review. PCSA criteria will determine which patients had at least 1 PCSA during the on-treatment period, taking into account all evaluations performed during the on-treatment period, including nonscheduled or repeated evaluations. The number of all such patients will be the numerator for the on-treatment PCSA percentage. The treatment-emergent PCSA denominator by group for a given parameter will be based on the number of patients assessed for that given parameter in the treatment-emergent adverse event period by treatment group on the safety population

The incidence of PCSAs during the on-treatment period will be summarized by treatment group irrespective of the baseline and/or according to the following baseline categories:

- Normal/missing.
- Abnormal according to PCSA criterion or criteria.

2.4.6.5 Analyses of electrocardiogram variables

Abnormalities analyses

For all parameters, an “on-treatment” analysis will be performed on the safety population, using all assessments during the TEAE period including any unplanned/rechecked values.

The same definition of PCSAs ([Appendix I](#)) will be used for all parameters, whatever the source. For the PCSAs on change from baseline in corrected QT data, in case a subject experienced multiple abnormalities, she will be counted only once in the most severe category.

Counts of subjects with PCSAs will be provided in summary tables regardless of the normal or abnormal status of the baseline. This table will be presented by treatment group.

Descriptive statistics and plots

For each of the ECG parameters, descriptive statistics on baseline and changes from baseline at each post-baseline time point will be provided by treatment group. Summary plots (mean +/- SEM) will be provided by visit and treatment group.

Validation of the QT correction

In order to explore whether the QTcF interval seem to be independent from the RR intervals, the plots of the QTcF intervals versus RR (using all replicates) will be provided, separately for off-drug and on-drug data, using ECGs send by core lab. The scatter plots, the regression line, and estimator of slope with 90% confidence interval (CI) will be provided, separately for off drug and on drug and in each treatment group.

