Viral serologies	X						Viral serologies include hepatitis A antigen or IgM hepatitis A antibody, HBs antigen or hepatitis B viral DNA, hepatitis C antibody or quantitative hepatitis C viral (HCV) ribonucleic acid (RNA).
Single 12-lead ECG	X						See Section 8.2.3 for details.
Triplicate ECG		X		X			Electronic records of triplicate ECG are required at pre-dose on D1 and at pre-dose and 3h post-dose on D14. See Section 8.2.3 for details.
Vital signs	X	(X)	X	X			These assessments will be repeated within 1 day prior to the first dosing of IMP if abnormal or if screening assessment >7 days of D1. See Section 8.2.2 for details.
Patient diary distribution		X					
Patient diary review			X	X			
Amcenestant administration 400 mg QD		Continuous once a day (QD)					Study treatment should be taken in the morning. Study treatment duration is planned for 14 days, and should not exceed 14 days. IMP will be dispensed at the study site visits on D1. On D1 and D14, IMP will be taken on-site after fasting tests and pre-dose assessment. See Section 6.1 for details.
Amcenestant administration 200 mg QD		Continuous once a day (QD)					
Letrozole administration		Continuous once a day (QD)					

Procedure ^a	Screening	Treatment Period (14 days)			Surgery ^c	Post treatment safety follow-up period	Notes
	up to 14 days before randomization	D1 ^b	D7 (±2)	D14	D15 (+1)	30 (±7) days after last IMP intake	
Tumor Biopsy ^d	X				X		Participant selection is based on the biopsy at diagnosis analyzed in a local lab. A new core-cut biopsy (baseline sample) should be performed prior to the first dosing of IMP, as well as a core-cut biopsy from surgery specimen or new core-cut biopsy after the last IMP intake for study purpose. Alternatively, tissue from the diagnostic biopsy may be used for the baseline sample if certain criteria are fulfilled. Baseline and post-treatment biopsy will be centrally examined. See Section 8.6.1 for details.
Tumor size by ultrasound	X			X			Measurement of tumor size using ultrasound at screening (baseline) and on D14. At screening, tumor size assessed by ultrasound will also be used for inclusion criteria. See Section 8.1.2 for details.

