2.1.4.5 Electrocardiogram variable

Triplicate electrocardiogram assessments will be described as normal or abnormal by central reading at pre-dose on Day 1 and at pre-dose and 3h post-dose on Day 14.

Single 12-lead ECGs will be recorded at screening by local assessment and investigator's opinion (normal/abnormal) will be reported.

The following parameters will be assessed/derived and provided for statistical analysis:

- PR (in ms)
- QRS (in ms)
- QT (in ms)
- Mean RR (in ms)
- QTcB (in ms) = $QT \cdot RR^{-0.50}$
- QTcF (in ms) = $QT \cdot RR^{-0.33}$
- Heart rate (in bpm) = $60/RR$ with RR in seconds

In case of triplicates assessments, only the mean of the triplicate will be presented. All parameters will be analyzed as raw data and absolute change from baseline (raw value at visit X - baseline value). In addition, for the abnormalities analyses and descriptive statistics, PR and QRS will be also analyzed as percent change from baseline ($100 \times [\text{raw value at visit X} - \text{baseline value}] / \text{baseline value}$). Semi-automatic reading from core lab of these quantitative parameters will be used for concentration-ECG analyses.

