2.4.9.2 Concentration-ECG analyses

Exploratory plots

The relationship between change from baseline of ECG parameters and SAR439859 concentrations will be first explored graphically, in order to investigate any potential delayed or sustained effects and the type of modeling to be done, using the following plots, by treatment group:

- Plot of mean (\pm SEM) change from baseline in ECG data and mean SAR439859 concentration versus time (hours post-dose) overlaid onto the same plot.
- A scatterplot for PK plasma concentration versus change from baseline in ECG parameter, including trend lines (simple linear regression and loess line)

Concentration - ECG analyses will be performed for the QTcF, heart rate, PR and QRS intervals.

Time-matched pharmacokinetic concentrations will be used.

Modeling

In case of direct and linear relationship between concentrations and change from baseline in ECG parameters (QTcF, HR, PR, and QRS), a linear mixed effect model will be carried out, with population intercept, fixed terms for nominal time, with the concentration (slope) and the baseline ECG parameter (centered baseline values: subject's baseline minus the mean of the overall population) as covariates, and with random terms for individual subject deviation from the population intercept and slope, using SAS Proc Mixed. The analysis model was the following:

Change from Baseline in ECG parameter_{ij} = ($\alpha + A_i$) + $\gamma \times$ Baseline ECG_i + C \times Time_j + $\beta \times$ Concentration_{ij} + e_{ij}

with:

- α and β are the fixed population intercept and concentration slope.
- γ is the fixed effect for the baseline ECG slope
- A_i is the random intercept for the i^{th} subject, with A_i assumed to be normally distributed with null mean and an unstructured variance-covariance matrix per subject block.
- C is the fixed effect associated with Time_j (0 for pre-dose of D14 and 1 for 3h post-dose of D14)
- e_{ij} represents i.i.d. standard normal errors.

The estimates of each effect of the model, along with their 95% confidence interval, will be provided. In addition, prediction of change from baseline in ECG parameters at selected concentrations (geometric mean concentration at 3h of D14 for each dose) will be also calculated from the model (estimates and 90% confidence intervals). The scatter plot of individual ECG values versus PK concentrations with the regression line overlaid will be also provided.

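### SAP 2.4.6.5 gives a 90% CI for the QTcF-RR slope from all ECG replicates without saying how repeated records on one patient are handled; on the natural reading the interval is too narrow

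*SAP*

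**What the plan says.** The aim in SAP 2.4.6.5 is modest: "In order to explore whether the QTcF interval seem to be independent from the RR intervals". To that end, "the plots of the QTcF intervals versus RR (using all replicates) will be provided, separately for off-drug and on-drug data". The output is then listed: "The scatter plots, the regression line, and estimator of slope with 90% confidence interval (CI) will be provided", and this is done "separately for off drug and on drug and in each treatment group". Two drug states and three arms make six slopes. The data are the core-laboratory ECGs, with every replicate used. No regression model, standard-error method, patient effect or clustering is named.

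The schedule in Protocol 1.3 fixes the number of records: "Electronic records of triplicate ECG are required at pre-dose on D1 and at pre-dose and 3h post-dose on D14". Protocol 8.2.3 places the three recordings of a triplicate within a five-minute span, with the patient supine.

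Elsewhere the SAP treats repeated ECGs differently. Section 2.1.4.5 states: "In case of triplicates assessments, only the mean of the triplicate will be presented". For the concentration-ECG analysis in 2.4.9.2, "a linear mixed effect model will be carried out", with random subject terms.

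**The concern.** Three ECGs taken minutes apart in one resting patient are likely to have similar RR and similar QTcF. If a single line is fitted through all of them and the usual regression interval is printed, each replicate counts as a new patient. The slope estimate stays unbiased, but its interval overstates what the data can say.

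This slope is the SAP's only check of QTcF against heart rate, and QTcF is the only corrected QT carried into the concentration-ECG model. With no acceptance rule, readers are likely to judge the slope by whether its interval contains zero, so the width carries the message. Enrolment also stopped early (SAP 2.4), which leaves fewer patients than planned with several records each.

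**Working it through.** The documents give no slope, standard error or correlation for this analysis, so there is no figure of theirs to reproduce. The check asks what simple regression on all records would do.

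**Inputs from the documents**
- Records per patient, m: one core-laboratory triplicate on Day 1, so m = 3 off drug; two on Day 14, so m = 6 on drug. The SAP does not define the two states, and this is the plain reading. The screening ECG is single and locally read, so it is not counted.
- Patients per arm: 42 planned (SAP 1.3). The actual number is lower and not given.

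**Assumed inputs**
- Within-patient intraclass correlations of RR (ρ_RR) and of the regression residual (ρ_e), varied from 0.3 to 0.9.

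**Formulas**, for m exchangeable records per patient
- Variance inflation of the pooled slope: DE = 1 + (m − 1) × ρ_RR × ρ_e
- True SE divided by printed SE: √DE
- Actual coverage of a nominal 90% CI: 2Φ(1.645/√DE) − 1

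Worked case, on drug with both correlations at 0.7: DE = 1 + 5 × 0.49 = 3.45; √DE = 1.86; 1.645/1.86 = 0.886; coverage = 62%.

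| ρ_RR / ρ_e | Off drug: DE | √DE | Coverage | On drug: DE | √DE | Coverage |
|---|---|---|---|---|---|---|
| 0.3 / 0.3 | 1.18 | 1.09 | 87% | 1.45 | 1.20 | 83% |
| 0.5 / 0.5 | 1.50 | 1.22 | 82% | 2.25 | 1.50 | 73% |
| 0.7 / 0.7 | 1.98 | 1.41 | 76% | 3.45 | 1.86 | 62% |
| 0.9 / 0.9 | 2.62 | 1.62 | 69% | 5.05 | 2.25 | 54% |

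**Limits.** If ρ_RR = 0, DE = 1 and nothing is lost. If both correlations are 1, √DE is √3 = 1.73 off drug and √6 = 2.45 on drug, with coverage 66% and 50%. These are the worst cases.

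**Effective number of records at 0.9 / 0.9 with 42 patients.** Off drug, 126/2.62 = 48; on drug, 252/5.05 = 50. Doubling the records adds almost nothing.

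**Simulation check** (4,000 data sets per setting, true slope zero, 42 patients)
- Off drug, coverage was 82%, 76% and 68% at correlations of 0.5, 0.7 and 0.9, in line with the formula.
- On drug, the two Day 14 triplicates may be less alike than the records within one triplicate. With within-triplicate and between-time-point correlations of 0.5/0.3, 0.7/0.5 and 0.9/0.7, coverage was 79%, 66% and 58%, somewhat above the exchangeable figures.
- Patient-clustered standard errors, with the factor n/(n − 1) and a t quantile on n − 1 degrees of freedom, gave about 87-89% with 42 patients and 85-88% with 20.

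**The case against.** The best defence is that the SAP does not state an error. A reader might infer that the plan treats the records as independent, but 2.4.6.5 does not say so. A mixed model or clustered standard errors would also fit its wording, and 2.4.9.2 shows that subject effects are used for ECG data where a model is specified. Nor does the triplicate-mean rule in 2.1.4.5 contradict it, because 2.4.6.5 makes an explicit exception for this plot. All of that stands. What remains is that a programmer asked for a regression line and slope interval on an all-replicate scatter would most naturally run simple regression, and nothing in the text would stop it.

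A reader might also infer that the slope decides whether the QTc results can be trusted, or that a sound correction could be declared invalid. The documents do not support this. There is no threshold, test or fallback correction. Section 2.4.9.2 uses QTcF whatever the slope shows, Appendix I applies its limits under any correction formula, and 2.1.4.5 derives QTcB as well. SAP 2.4 makes confidence intervals descriptive, in a sentence prompted by the dropped primary test but worded generally. A descriptive interval should still describe the uncertainty, but no planned decision depends on this one.

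Finally, calling the interval far too narrow as a matter of fact goes beyond the evidence. High correlation is plausible for records minutes apart, but it is assumed here, and at 0.3/0.3 the loss is small.

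**Conclusion.** The point holds as a minor one. The SAP reports a slope with a 90% CI from 3 or 6 scheduled records per patient and leaves the handling of their correlation open. If simple regression is used, actual coverage is about 69-87% off drug and 54-83% on drug for assumed correlations from 0.9/0.9 down to 0.3/0.3. The on-drug figures are somewhat better if the two triplicates are less correlated with each other, and there is no loss if RR does not correlate within patients. The direction is certain whenever both correlations are positive; the size is not known from the documents. The analysis is exploratory and the primary endpoint is untouched. The gain is an honest interval on the one check of QTcF against heart rate.

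**What to change.** Add one sentence to SAP 2.4.6.5: the 90% CI of each slope is computed from patient-clustered standard errors with a small-sample correction. This leaves the fitted line unchanged and alters only the interval. The correction matters because enrolment stopped early. The simple one used in the check still fell short of 90% with 20 patients, so a stronger form, such as bias-reduced (CR2) standard errors with Satterthwaite degrees of freedom, is worth naming.

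A linear mixed model with random effects for patient and for time point within patient is an alternative in keeping with 2.4.9.2. It is not interchangeable with clustering, because it reweights within- and between-patient information and so can move the slope itself. Triplicate means alone are not enough: they leave one point per patient off drug but still two correlated points on drug.

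Keep the all-replicate scatter as the display. The cost is that sentence, a change to one analysis call and a wider interval. No new data are needed.

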2.4.7 Analyses of pharmacokinetic and pharmacodynamic variables

2.4.7.1 Analysis of Pharmacokinetic variables

Plasma concentrations will be summarized for each SAR439859 treatment arm by time point using descriptive statistics (such as the number of observations, arithmetic and geometric mean, median, standard deviation (SD), standard error (SE), coefficient of variation (CV)%, minimum, and maximum).

Plasma concentrations will be included in the descriptive statistics if actual sampling occurs in the following predefined time windows: within 2 hours before administration for predose sample on Day 7, Day 14, [2-4h] for samples at 3h post dose on Day 14 and Day 15;

In addition, a listing of individual concentration data by time and day will be provided.

Concentrations reported as below the limit of quantification (BLQ) will be replaced by 0 for descriptive statistics.

In case PK parameters estimates are calculated and used as part of the PK/PD exploratory analysis, they will be summarized by SAR439859 treatment arm using descriptive statistics (such as the number of observations, arithmetic and geometric mean, median, standard deviation (SD), standard error (SE), coefficient of variation (CV)%, minimum, and maximum).

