1. Incorporate mandated Clinical Trial Facilitation Group (CTFG) guidance to clarify the requirement of FSH measurements to confirm postmenopausal status;
2. Include contingency measures for a regional or national emergency, as declared by a governmental agency;
3. Update the inclusion/exclusion criteria, prohibited concomitant medications and AESI according to the new available data from ongoing amcenestant studies;
4. Optimize the PK assessment time points for amcenestant.

Protocol amendment summary of changes table

Section # and Name	Description of Change	Brief Rationale
1.3 Schedule of Activities (SOA): notes of FSH test & 5.1 Inclusion criteria I04 b)	Updated the protocol verbiage to reflect serial FSH measurements are required to confirm postmenopausal status for the patients who have received hormonal replacement therapy but have discontinued this treatment and in the absence of amenorrhea >12 months.	In line with the recommended Clinical Trial Facilitation Group (CTFG) guidance dated 2014, multiple FSH measurements (at least two) to confirm postmenopausal state should be conducted before including women in the absence of amenorrhea >12 months.
1.3 Schedule of Activities (SOA): footnote d; & 8.6.1 Tumor biopsy Section 8.8.1 Protein Biomarkers	Added Cyclin D1 in the exploratory protein biomarker panel to be tested by IHC in tumor tissues.	To complement data on impact of amcnestant and letrozole on cell cycle arrest in addition to Ki67, since Cyclin D1 is regulated by ER.
3 Objectives and endpoints: Table 1; & 8.6.1 Tumor biopsy	Added Complete Cell Cycle Arrest (CCCA) as an exploratory endpoint to further assess impact on proliferation; and added digital assessment of protein biomarkers.	To add some additional tools to evaluate impact on proliferation, and to explore increased reproducibility and objective measurement of protein expression.
1.3 Schedule of Activities (SOA)	Removed PK sampling on Day 1 and Day 7, and added PK sampling on Day 15.	To optimize the PK sample collection time points. So that an on-site visit could be changed to a remote visit whenever possible (especially during pandemic).
5.1 Inclusion criteria I01	Added "or country's legal age of majority if the legal adult age is >18 years old".	To adapt some local country's law.

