Pathological tumor (pT) stage, the pathological node (pN) stage, pCR and ECOG response assessment, Preoperative Endocrine Prognostic Index (PEPI)					X		Pathological tumor (pT) stage, the pathological node (pN) stage, and pCR results will be collected from the local pathologist's report following examination of tissue (breast and nodes) removed at the time of surgery and reported in eCRF. ECOG response will be assessed by the investigator according to ECOG response criteria. See Section 8.1.1 and Section 8.1.3 for details.
AE/SAE review	←=====→						AEs of new onset as well as worsening of baseline signs and symptoms are to be reported from the signing of the informed consent to 30 (±7) days following the last IMP intake. All SAEs, and non-serious AEs of special interest, and non-serious AEs related to IMP still ongoing at the post treatment safety follow-up visit, will be followed until resolution, stabilization, the event is otherwise explained, or the participant is lost to follow-up. See Section 8.3 for details.
Concomitant medication	←=====→						The period of collection of concomitant medications extends from the signing of the informed consent to 30 (±7) days following the last IMP intake. See Section 6.5 for details.

Procedure ^a	Screening	Treatment Period (14 days)			Surgery ^c	Post treatment safety follow-up period	Notes
	up to 14 days before randomization	D1 ^b	D7 (±2)	D14	D15 (+1)	30 (±7) days after last IMP intake	
Genetic sample (plasma for cfDNA)		X		X			cfDNA sample collected on D1 and D14. See Section 8.7 for details.
Genetic sample (saliva for reference DNA)		X					Saliva will be collected on D1 to extract DNA which will be used as a normal reference for the mutation analysis. See Section 8.7 for details
Genetic sample (blood for DMET genotyping)		X					Blood sample will be collected on Day 1 for amcenestant treatment arms only. See Section 8.7 for details
Amcenestant PK				X	X		PK sampling is planned only for amcenestant treatment arms. D14: Pre-dose (P00), T3h post dose (P01) D15: T24h post dose (P02) after last administration of amcenestant (D14) When PK and triplicate ECG are scheduled at the same time, PK sample will be taken just after ECG recording. Participants will take IMP on-site on days of PK sampling. See Section 8.5 for details.

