8.5 PHARMACOKINETICS

- Pharmacokinetic sampling is planned only in participants randomized in amcenestant treatment arms.
- Blood samples of approximately 1 mL will be collected for measurement of plasma concentrations of amcenestant as specified in the SoA ([Section 1.3](#)) using a validated liquid chromatography-mass spectrometry/mass spectrometry assay. Instructions for the collection and handling of PK samples will be provided by the Sponsor in the laboratory manual.
- Samples will be used to evaluate the PK of amcenestant. Samples collected for analyses of amcenestant plasma concentration may also be used to evaluate safety or efficacy aspects related to concerns arising during or after the study.
- It is of utmost importance to collect all blood samples at the specified time windows and according to the specifications (refer to the laboratory manual).
- Samples missed or lost for any reason should be recorded. Actual dates and times (24-hour clock time) of blood collection should be recorded. Actual dates and times of previous drug administration should also be precisely recorded.

For the comfort of the participants, some PK samplings may be deleted during the course of the study if they are no longer deemed necessary by the Sanofi PK team.

Any changes in the timing or addition of time points for any planned study assessments must be documented and approved by the relevant study team member and then archived in the Sponsor and site study files but will not constitute a protocol amendment. The IRB/IEC will be informed of any safety issues that require alteration of the safety monitoring scheme or amendment of the ICF.

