2.1.5 Pharmacokinetic variables

SAR439859 plasma concentrations will be determined at the predefined time point according to the SoA presented in Section 1.3 of the protocol.

In addition, population PK approaches might be used to calculate individual PK parameters estimates. The population PK analysis, if any, will be described in a separate report.

PK concentrations (and potentially PK parameter estimates) will be used to conduct an exploratory PK/PD relationship analysis of SAR439859 with pharmacodynamics (eg, Ki67) and/or safety (eg, triplicate ECG parameters, incidence of AEs).

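### As printed, SAP 2.4.7.1 gives no inclusion window for the scheduled Day 15 24 h PK sample, and its BLQ = 0 rule would spoil a geometric mean if any BLQ value occurs

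*SAP*

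**What the plan says.** SAP 2.4.7.1 calls for concentrations to be summarized by amcenestrant arm and time point, and makes inclusion depend on actual sampling time: "Plasma concentrations will be included in the descriptive statistics if actual sampling occurs in the following predefined time windows". The first window is "within 2 hours before administration for predose sample on Day 7, Day 14". The second is the 2 to 4 h window, given as "2-4h] for samples at 3h post dose on Day 14 and Day 15". The sentence then stops at a semicolon. No window near 24 h is printed.

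For which samples exist, SAP 2.1.5 defers to the protocol: concentrations are "determined at the predefined time point according to the SoA presented in Section 1.3 of the protocol". That schedule (Protocol 1.3, amcenestrant PK row) has three samples: P00 before the Day 14 dose, P01 at 3 h after it, and on the next day "D15: T24h post dose (P02", timed from the Day 14 dose. On treatment length the same schedule says: "Study treatment duration is planned for 14 days, and should not exceed 14 days".

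SAP 2.4.7.1 also names the geometric mean among its summary statistics and replaces BLQ concentrations by 0 for descriptive statistics. SAP 2.4.9.1, for the PK/PD graphs, replaces values below the lower limit of quantification (LLOQ) by LLOQ/2.

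**The concern.** An inclusion window decides which values enter a table. If the only window printed for Day 15 is 2 to 4 h after a dose, and the only Day 15 sample is scheduled at 24 h, a programmer who follows the text leaves P02 out of the summary. A programmer who follows the evident intent puts it in, with no stated limit on sampling time. Either way the choice is made outside the plan.

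The limit has some practical weight because P02 sits in the surgery column of the schedule. Surgery is set for Day 15 (+1) and may exceptionally be as late as 48 h after the last dose (Protocol 1.3, footnote c). A row labelled 24 h with no window could mix concentrations taken a day apart.

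The BLQ rule is a separate matter. A zero is workable for an arithmetic mean or a median, but not for a geometric mean.

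**Working it through.** **Windows against samples.** There is no stated figure to reproduce, so the check sets the two documents side by side.

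| Sample in the current schedule | Nominal time | Window in SAP 2.4.7.1 | Admitted? |
|---|---|---|---|
| P00, Day 14 | before the Day 14 dose | within 2 h before dosing | yes |
| P01, Day 14 | 3 h after the Day 14 dose | 2 to 4 h | yes |
| P02, Day 15 | 24 h after the Day 14 dose | none that fits | no |

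P02 lies 24 - 4 = 20 h past the upper limit of the only window that mentions Day 15. Counting that window from the Day 14 dose does not help, because 2 to 4 h after that dose is not Day 15. Counting it from a Day 15 dose does not help either: no 3 h sample is scheduled that day, and P02 is defined from the Day 14 dose. So 2 of 3 scheduled samples have a window and 1 of 3 has none.

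**Why a stated width matters for P02.** Inputs: terminal half-life around 20 h (Protocol 4.3), with 18 to 24 h taken here as an assumed range, and possible sampling from 24 to 48 h after the last dose. With mono-exponential decay, C(48)/C(24) = 2^(-24/half-life):

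- 18 h: 2^(-24/18) = 0.40
- 20 h: 2^(-24/20) = 0.44
- 24 h: 2^(-24/24) = 0.50

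A sample at 48 h would be about 40% to 50% of its 24 h value.

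**BLQ set to 0.** Assumed values in arbitrary units: 19 concentrations of 100 and one BLQ value.

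- Arithmetic mean with BLQ = 0: 1900/20 = 95.
- Geometric mean with BLQ = 0: (100^19 x 0)^(1/20) = 0, or undefined if computed through logarithms.
- Geometric mean with LLOQ/2, assumed LLOQ 1: 100 x (0.5/100)^(1/20) = 76.7.
- Geometric mean with LLOQ/2, assumed LLOQ 5: 100 x (2.5/100)^(1/20) = 83.2.

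One zero is enough whatever the number of other values. The substituted result still moves with the assumed LLOQ, so the count of BLQ values should be reported beside it.

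Neither document gives an LLOQ or a BLQ rate. For 40 samples at a time point (the planned evaluable number per arm, which SAP 2.4 says will not be reached) and independent samples, the chance of at least one BLQ value is 1 - (1 - p)^40. For assumed rates p of 0.5%, 1%, 2% and 5% this is 18%, 33%, 55% and 87%. Fewer samples give lower chances.

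**The case against.** **The sentence may be incomplete.** It ends in a semicolon, so Day 15 may have opened a further item whose window was lost in drafting or in conversion of the PDF. This stands. It is why the point is confined to the text as printed, why confidence is moderate, and why the first step is to look at the source file.

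**The schedule may imply a Day 15 dose.** A sentence in the same PK note has participants take study drug at the site on PK sampling days. Read literally, that includes Day 15. It conflicts with the 14-day limit and with the dosing note that names only Day 1 and Day 14 for on-site intake, and these passages must be reconciled. It does not rescue the window, since it creates no 3 h sample on Day 15.

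**The Day 7 window looks like an error too.** A reader might infer this because the current schedule has no Day 7 PK sample. The documents do not support it: Amendment 02 is recorded as "Removed PK sampling on Day 1 and Day 7, and added PK sampling on Day 15", so participants treated earlier may have Day 7 concentrations for that window to admit.

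**BLQ values are unlikely.** All current samples follow repeated daily dosing at 200 or 400 mg, the half-life is around 20 h, and Protocol 7.1.1 drops PK sampling after early discontinuation. The geometric mean is also one item in a list of example statistics, and LLOQ/2 in SAP 2.4.9.1 serves graphs, so having two rules is not in itself a contradiction. All of this stands, and it makes the point conditional. It does not make 0 usable in a geometric mean. For Ki67, SAP 2.4.5.1.1 guards against exactly this by adding 0.1% to zero values before taking logs.

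**Conclusion.** The point holds as a minor correction, with moderate confidence. As printed, no window admits P02, which is 1 of 3 scheduled samples per amcenestrant participant. The number of samples affected cannot be derived, because enrollment stopped early and participants treated before Amendment 02 may have no P02.

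A reader might go further and infer that the Day 15 data are lost to the study. The documents do not support that. SAP 2.4.7.1 also provides a listing of individual concentrations, SAP 2.4.9.1 states no window for the PK/PD graphs, and the concentration-ECG model in SAP 2.4.9.2 uses only the two Day 14 times. Under once-daily dosing the Day 14 pre-dose sample is itself a nominal 24 h trough and is summarized, so little information is at risk.

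Nor do the documents support saying that the requested geometric means fail outright: they fail only at a time point with at least one BLQ value. SAP 2.4.9.2 predicts ECG changes at the geometric mean 3 h concentration for each dose. It does not say whether that figure comes from this summary; if it does, the same condition applies.

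The effect is confined to descriptive PK output for an exploratory objective. The Ki67 analysis is unaffected.

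**What to change.** Before database lock:

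1. Check the SAP source file for a clause after the semicolon in 2.4.7.1.
2. Limit the 2 to 4 h window to the Day 14 3 h sample.
3. Add a window of sponsor-defined width around 24 h after the Day 14 dose for P02. Samples outside it appear in the listing only.
4. Keep the Day 7 pre-dose window only for participants sampled before Amendment 02, and label that row accordingly.
5. For geometric means, use a nonzero BLQ substitution, for example LLOQ/2 as in SAP 2.4.9.1, and report the number of BLQ values at each time point.
6. Reconcile the schedule's sentence on study drug intake on PK sampling days with its 14-day limit.

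The SAP changes amount to one sentence, one programming filter and one BLQ rule; item 6 is a clarification of the protocol text. No new data are needed. Protocol 8.5 already asks that actual dates and times "of blood collection should be recorded. Actual dates and times of previous drug administration should also be precisely recorded", and SAP 2.3.5 requires documented dosing and sampling times for the PK-evaluable population.
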